The primary aim of our study is to evaluate whether the application of the tape with lymphatic technique to the fingers, both dorsal and volar, of wrist fractured patients treated with a forearm circular plaster cast is able to reduce the formation of hand oedema, compared to the untreated controls. Furthermore, we aim to assess the differences in pain and cast tolerability between the intervention group and the control group.

Primary endpoints

(i) difference in the circumference of the thumb between baseline (T0) and 7-days follow-up (T1), and (ii) difference in the circumference of the remaining 4 fingers merged together, between T0 and T1.

Secondary endpoints

(i) pain intensity at T0 and T1, (ii) analgesic use during the previous 4 hours at T0 and T1, and (iii) OER re-entry number for “intolerance to the plaster cast”.

Design

Our study is a randomized controlled superiority trial, with parallel design and blinded data processing, developed at OER of Local Health Unit of Piacenza.

The ID NCT04683887 identify this study on clinicaltrials.gov.

Participant characteristics

The patients' eligibility criteria to participate in our study are described in Table 1.

Sample size calculation

The sample size was calculated using the GPower 3.1 Software, setting the following parameters: effect size: 0.4, error α = 0.05, power = 0.80 and allocation ratio = 1.

The resulting sample size is 100 subjects per arm; the number of patients to be enrolled will be a total of 220 (110 per group), taking into account a 10% loss to follow up. The choice of medium effect size (0.4) was made based on feasibility and available literature (Gülenç et al., 2019; Pajero Otero et al., 2019; Tantawy et al., 2019) despite the absence of similar studies for pathology/type of intervention/primary endpoint.

Setting

Patient enrolment, execution of the fracture reduction maneuver, application of the plaster cast, application of the tape for the investigational treatment patient group, and endpoint T0 measurements will take place at the OER service of Local Health Unit of Piacenza. On day 7 the

tapes will be removed and endpoint T1 measurements will be assessed at the Orthopedics and Traumatology outpatient clinic.

Preliminary procedures and nurses' training

Before the enrolment of the first patient, all OER nurses will be trained for the tape application by a certified instructor.

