All OER orthopedic doctors and nurses are trained and skilled in the closed reduction technique and forearm circular cast application. The closed reduction technique, done manually by three operators, and circular cast application are performed as described in Dresing et al. (2017).

Patients' enrolment

After having performed the necessary radiographic investigations and verified the presence of all inclusion criteria and the absence of exclusion criteria, complete oral and written information about the study will be given to each patient by OER nurses and physicians. A reflection period will be guaranteed to the patient during the waiting time before the control X-ray after reduction procedure.

Enrolment will be effective as soon as the patient has signed the consent form. We will then assign him/her to the intervention or control group after a telephone call to the Data Analysis Manager, as described in the following section.

Randomization, blind and control

We will generate the randomization list through the program called "Random Number Generator", available at <https://stattrek.com/statistics/random-number-generator.aspx>. The randomization will be simple with 1:1 allocation. The randomization list, known only to the Data Analysis Manager not involved in the clinical evaluation of patients, will be implemented and hidden inside a specific file protected by a password to prevent identification of the patient. We will assign the enrolled patients to group 0 or 1 according to the list by a telephone contact between Investigators and Data Analysis Manager.

The data-analyzing Researcher will not know which of the two groups will be the intervention nor the control one, to guarantee the blind. The Investigators are not allowed to collect data in a blind way due to the nature of study intervention.

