We decided not to apply any type of alternative strip to the control group. Even if positioned without lymphatic technique, the tape would maintain its elastic properties and we cannot exclude that it may still have an effect. The application of a strip with properties different from the tape on one side would still have the adhesive effect induced by the glue-skin interaction, stimulating muscle function (Blow, 2015; Frignani, 2017; Zimiglia, 2014), but on the other hand, having a different elasticity from that of the tape, could reduce the range of motion (ROM) of the fingers (Frignani, 2017) and potentially could increase the risk of developing oedema in the control group.

Outcome evaluation details

OER nurses will evaluate the extent of oedema in the fracture-homolateral hand by measuring the circumference at the base of the 1st phalanx of the 1st finger and at the base of the 1st phalanx of the remaining 4 fingers merged together both at T0 and T1. The number of re-entries in OER between T0 and T1 will be registered. Furthermore, we will measure the intensity of pain with the Numerical Rating Scale (NRS) (Artioli et al., 2016; Peate et al., 2018) both at T0 and T1. At T0, the pain will be assessed before the possible administration of local anesthetic, while we do not expect differences between the intervention and the control group. Finally, the eventually analgesic use during the previous 4 hours will be recorded both at T0 and T1.

Procedure

An alphanumeric code will identify each patient in the case report form (CRF) and in the electronic database used for the analyzes, in order to guarantee pseudonymization.

We will report in the CRF the variables described in the Table 2.

Once the fracture reduction maneuver has been performed and the immobilization performed in a plaster cast, if the patient belongs to the intervention group, we will apply the tape only to the fingers of the hand with a lymphatic technique (Figure 2). We will not extend the application to the

metacarpals even if it would increase the surface of action, because portions of the tape will remain under the plaster, hiding possible skin reactions to the glue. Moreover, the tape application up to the metacarpals, inevitably performed before cast application, will increase the risk of detaching during the plaster wrap.

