Blow (2015) suggests that the tape application needs to be proximal to the plaster cast. However, this indication is not supported by the literature. Other authors apply tape on the area that will probably form oedema (Donec, et al.,2014). Therefore, we believe that tape application on hand fingers is the most appropriate for achieving the objectives of this study.

The tape available at the Local Health Unit of Piacenza is the Leukotape K® by Essity, winner of the INTERCENTER AVEN tender for the supply of this type of medical device.

CRFs will be kept in OER until follow-up, so that any re-attendances can be noted.

Follow up

Even though tape results could be seen after 2-3 days, we choose to collect T1 variables (as previously described) at day 7 in order to avoid possible bias in the re-entry evaluation. The 7-day follow-up will be concomitant with the radiographic fracture control provided by organization procedure.

The completed CRFs will be delivered to the Researcher who will carry out the data analysis.

Statistical analysis

We will describe the general characteristics of the two groups. We will evaluate the effectiveness of randomization through the χ^2 test, for categorical variables, and the t-test, for continuous variables. Intervention group versus control group analyses will be performed by comparing the respective mean of: the T0-T1 differences of circumference of both thumb (*i*) and the other 4 fingers (*ii*), the pain NRS score at T1(*iii*), and the number of OER re-entries (*v*), by t-test for independent groups (after verifying the normality of the distributions with the Shapiro Wilk test).

All analyses will be performed on an Intention-To-Treat principles: all randomized patients will be analyzed in the arm they were allocated by randomization. Only screening failures and patients

who refuse before the treatment start would be excluded. In the event of tape detachment in the first 48 hours after T0 and/or impossibility to evaluate study endpoints, missing data will be substituted by multiple imputation.

We will perform all analyzes using 2-tailed tests and consider significant a p value <0.05. We will report all analyzes according to the international guidelines for RCTs (Boutron et al., 2017).

REFERENCES

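### The intention-to-treat rule lets a patient who refuses after an open allocation be dropped, most naturally only in the tape arm, and treatment start is never defined

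*Combined protocol and SAP*

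**What the plan says.** The Statistical analysis section applies intention-to-treat to all analyses: "all randomized patients will be analyzed in the arm they were allocated by randomization". The next sentence makes an exception for screening failures and for patients "who refuse before the treatment start would be excluded". It does not say what counts as treatment start.

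Other parts of the protocol fix the setting of that exception:

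- **Patients' enrolment:** once consent is signed, "We will then assign him/her to the intervention or control group after a telephone call to the Data Analysis Manager".
- **Procedure:** after reduction and casting, "if the patient belongs to the intervention group, we will apply the tape only to the fingers of the hand".
- **Setting:** the list of activities includes "application of the tape for the investigational treatment patient group", so the plan's own wording ties treatment to tape.
- **Randomization, blind and control:** "We decided not to apply any type of alternative strip to the control group". On blinding: "The Investigators are not allowed to collect data in a blind way due to the nature of study intervention". Only the researcher who analyses the data is blind.
- **Statistical analysis, missing data:** where the tape detaches within 48 hours or endpoints cannot be evaluated, "missing data will be substituted by multiple imputation". Refusers are not mentioned.

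**The concern.** The exception is tied to treatment start and not to randomisation, so it can reach patients whose arm is already fixed and known. A patient who hears the assignment to tape and declines it has been randomised but has not started the tape. A control patient has no study procedure to decline.

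Willingness to have injured fingers taped may be related to swelling or pain. If it is, the two analysed groups are no longer those that randomisation produced. Multiple imputation does not help, because an excluded patient is not in the set to be imputed. The rule covers all analyses, so both circumference endpoints and the secondary endpoints are exposed. If the refusers' day-7 data are never collected, the loss cannot be repaired later.

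**Working it through.** **1. What each reading of treatment start does**

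| Reading | Effect on randomised patients |
|---|---|
| Tape application | A tape-arm refusal after the call is excluded; controls have no counterpart |
| Cast, with allocation after the cast | Nobody is excluded; the rule is empty |
| Cast, with allocation before the cast | Both arms have the point, but any exclusion is still after open randomisation |
| Refusal before randomisation only | No harm, but the exception is redundant, since such patients are not among the randomised |

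The order of call and cast is not settled. The Setting section lists enrolment ahead of reduction and cast, while Patients' enrolment places the reflection period in the wait for the X-ray after reduction. The wording of the Setting section favours the first reading.

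**2. The plan's own figure**

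Inputs from Sample size calculation and Statistical analysis: effect size 0.4, two-sided alpha 0.05, power 0.80, ratio 1:1. The normal approximation gives n = 2(1.960 + 0.842)²/0.4² = 98.1, so 99 per arm. The exact noncentral t gives power 0.7997 at 99 and 0.8036 at 100, so 100 per arm, as stated. The enrolment target is 100 × 1.10 = 110 per arm, 220 in total.

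**3. Size of the possible bias**

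The documents give neither a refusal rate nor the prognosis of refusers, so both are assumed:

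- f = fraction of the tape arm removed: 2%, 5%, 10% (2.2, 5.5, 11 of 110).
- g = difference in untreated outcome between refusers and the rest of the arm: 0.25, 0.5, 1.0 SD.

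If the rest have mean m, the full arm has mean (1 − f)m + f(m + g) = m + fg. Removing the refusers leaves m, so the between-arm difference shifts by f × g in absolute size. With no true effect, the type I error comes from the noncentral t with noncentrality fg / √(1/[110(1 − f)] + 1/110), taking unit SD in both arms.

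Example, f = 10% and g = 1: 99 versus 110 patients; √(1/99 + 1/110) = 0.1385; noncentrality 0.10/0.1385 = 0.72; type I error 11.1%.

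| f | g (SD) | Shift (SD) | Share of 0.4 | Type I error |
|---|---|---|---|---|
| 2% | 0.25 | 0.005 | 1.2% | 5.0% |
| 2% | 0.5 | 0.010 | 2.5% | 5.1% |
| 2% | 1.0 | 0.020 | 5.0% | 5.3% |
| 5% | 0.25 | 0.0125 | 3.1% | 5.1% |
| 5% | 0.5 | 0.025 | 6.2% | 5.4% |
| 5% | 1.0 | 0.050 | 12.5% | 6.5% |
| 10% | 0.25 | 0.025 | 6.2% | 5.4% |
| 10% | 0.5 | 0.050 | 12.5% | 6.5% |
| 10% | 1.0 | 0.100 | 25.0% | 11.1% |

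**4. Price of keeping refusers in the tape arm**

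Assume that refusers get no tape effect, so the effect becomes 0.4(1 − f).

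| f | Diluted effect | Power, 110 analysed per arm | Power, 100 analysed per arm |
|---|---|---|---|
| 0% | 0.400 | 84.0% | 80.4% |
| 2% | 0.392 | 82.5% | 78.8% |
| 5% | 0.380 | 80.1% | 76.2% |
| 10% | 0.360 | 75.7% | 71.7% |

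**The case against.** The strongest reply is that screening failures and refusers, named together, simply mean people who never entered the trial. That reading treats both arms alike and agrees with the sentence before it. The flowchart listed as Figure 1 might have shown this, but it is not visible in the text. The reading is possible, but the text sets the limit at treatment start, and on this reading the exception would do nothing. What stands is that the authors may have meant something harmless, so the point is about the rule as written.

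A second reply is that refusals will be few. Patients consent after information and a reflection period, and the tape is applied at the same service. This also stands: at 2% the type I error barely moves.

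A reader might go further in four ways that the documents do not support:

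- **That every untaped patient is deleted.** The rule names refusers; a patient left untaped for another reason stays in the set.
- **That the bias favours tape.** The primary endpoints are changes from T0 to T1, and a hand already swollen at T0 may swell further or subside.
- **That the type I error reaches about 15% or 33%.** Such figures arise in simulation if 6 or 11 patients are removed and refusal picks out exactly the worst outcomes in the tape arm, a gap of about 2 SD. That is an upper bound, not an expectation.
- **That screening failures will occur after the call.** Patients' enrolment has all criteria verified before the patient is informed, and nothing describes a later failure.

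**Conclusion.** The contradiction holds: two adjacent sentences define different analysis sets, and the second permits exclusion after an open allocation. That the exclusion falls on the tape arm alone is a well-supported inference from an undefined term, not something the protocol states. If the cast is the treatment start, both arms share the point, yet any exclusion of an allocated patient is still post-randomisation.

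The bias could lie anywhere from negligible to about 0.10 SD, a quarter of the planned effect, with type I error from 5.0% to about 11%. These limits rest on the assumed ranges for refusal (2-10% of the tape arm) and prognosis (0.25-1.0 SD), and the direction is unknown. This should be fixed, because it concerns the definition of the primary analysis set, but the documents do not show that the trial's result would be seriously distorted. Confidence in the size is medium.

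**What to change.** Replace the exclusion sentence with:

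> *Only patients who fail screening or refuse before the allocation call are excluded. Every patient assigned by the call is analysed in the assigned arm, whether or not the tape was applied. T1 data are collected at the routine day-7 visit unless consent to data collection is withdrawn, and endpoints not obtained are multiply imputed.*

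Report refusals by arm, and check the analysis set against the randomisation list held by the Data Analysis Manager. Where the workflow allows, measure T0 circumferences before the call, so that a refuser has a baseline.

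The cost is a few sentences. The Follow up section already ties day 7 to the radiographic control, so no extra visit is needed, and the target of 220 need not change. The downside is slight dilution: if 5% of the tape arm are untaped, the effect falls from 0.40 to 0.38 SD, with power about 80% at 110 analysed per arm and 76% at 100.

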* Further exclusion criteria introduced following advices of Blow and Kumbrink although to date there are no absolute contraindications to the application of elastic tapes (Blow, 2015; Kumbrink et al., 2019).

Table 2: Variables of study CRF and study timepoints.

Variable name	Unit of measurement or possible categories	T0 (day1)	T1 (day7)
Subject code	N/A	X	
Gender	Male/Female	X	
Age	Years	X	
Heart disease	Presence/Absence	X	
Kidney pathologies	Presence/Absence	X	
Respiratory diseases	Presence/Absence	X	
Diabetes	Presence/Absence	X	
Hypertension	Presence/Absence	X	
Assigned group	0/1	X	
Fractured limb	Right/Left	X	
1 st finger circumference	Cm	X	X
Circumference of the remaining 4 fingers merged together	Cm	X	X
NRS	0-10	X	X
Analgesic use during the previous 4 hours	Yes/No	X	X
Accidental removal in the 48 hours after T0	Presence/Absence		X
Accidental removal	Presence/Absence		X
OER re-attendance between T0 and T1	Natural number		X

FIGURE LEGENDS

Figure 1. CONSORT flowchart modified for Randomized Trials of Nonpharmacologic Treatments (Boutron et al., 2017)

Figure 2. Tape application: a. lateral view, b. sight fly, c. dorsal view

FIGURES

[figure not shown]

Figure 1

Figure 2.

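### The plan does not say whether a day-7 value measured after early tape detachment is kept or imputed; if imputed, only the tape arm changes and the result is no longer the effect of assignment

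*Combined protocol and SAP*

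**What the plan says.** All locations are in the combined protocol and SAP.

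- **Statistical analysis, principle.** The analysis is by intention-to-treat: "all randomized patients will be analyzed in the arm they were allocated by randomization". Exclusions are limited to people who fail screening or refuse before treatment starts.
- **Statistical analysis, next sentence.** "In the event of tape detachment in the first 48 hours after T0 and/or impossibility to evaluate study endpoints, missing data will be substituted", the method being multiple imputation. Early detachment and non-evaluable endpoints are two triggers joined by *and/or*.
- **Randomization, blind and control.** "We decided not to apply any type of alternative strip to the control group".
- **Setting.** On day 7 the "tapes will be removed and endpoint T1 measurements will be assessed at the Orthopedics and Traumatology outpatient clinic". The Follow up section ties this visit to the routine radiographic control.
- **Sample size calculation.** Enrolment is raised from 100 to 110 per group, "taking into account a 10% loss to follow up".
- **Table 2.** The case report form has a field "Accidental removal in the 48 hours after T0" and a second field for accidental removal with no time limit. Both are recorded at T1, alongside the circumference measurements.

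The plan does not say what happens to a T1 circumference that was measured in a patient whose tape came off in the first 48 hours.

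**The concern.** An intention-to-treat analysis compares the outcomes of everyone as randomised, whatever happened to the treatment afterwards. Detachment happens after randomisation and can occur in one arm only. If it is enough to send a patient's outcome to imputation, keeping that patient in the allocated arm does not preserve the effect of assignment, because the outcome analysed is no longer the one observed. The estimate moves toward the effect in patients whose tape stayed on for at least 48 hours, and a reader would still take it as the effect of assigning tape. The clause applies to both primary endpoints.

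If the clause reaches only values that were never obtained, nothing is distorted. The rule is then merely unclear, and its meaning could be settled after the data are seen.

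**Working it through.** **1. Can detachment itself make T1 missing?** The T1 visit takes place on day 7 for both arms and coincides with a radiographic check that does not depend on the tape. Finger circumference can be measured without tape. Patients who do not attend fall under the second trigger, and the sample size already allows 10% for loss. So the detachment trigger reaches further than the second one only where a T1 value was measured.

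**2. The plan's own figure.** Inputs from Sample size calculation: effect size 0.4, α 0.05, power 0.80, ratio 1; two-sided from Statistical analysis. The exact two-sample t calculation gives power 79.97% at 99 per arm and 80.4% at 100, so 100 per arm is reproduced. Effects below are in SD of the T0–T1 difference.

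**3. Illustration A: tape works, benefit lost on early detachment.** Let p be the proportion detaching in the first 48 hours. The documents give no p, so 2%, 5% and 10% are assumptions.

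- Effect of assignment = 0.40 × (1 − p).
- Imputing the detached patients from the rest of the tape arm returns about 0.40, if detachment is unrelated to outcome given the model.

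| p | Effect of assignment | Within-arm imputation | Overstated by |
|---|---|---|---|
| 2% | 0.392 | about 0.40 | 0.008 |
| 5% | 0.38 | about 0.40 | 0.02 |
| 10% | 0.36 | about 0.40 | 0.04 |

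The imputation model also matters. One that ignores arm gives 0.40(1 − p) + p × 0.40(1 − p)/(2 − p). At p = 10% this is 0.36 + 0.10 × 0.36/1.90 = 0.379, an overstatement of 0.019.

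**4. Illustration B: no true effect, detached patients would swell 0.5 SD more anyway (assumed).** Removing them from the tape arm only, with within-arm imputation, gives a bias toward tape of p × 0.5, which is 0.05 SD at p = 10%. With about 90 informative tape values against 100 controls, the standard error is √(1/90 + 1/100) = 0.145 and the shift is 0.05/0.145 = 0.34 standard errors. The noncentral t tails are 5.3% (for tape) and 1.1% (against), about 6.4% in total. Simulating the full imputation with Rubin's rules (20,000 trials) gave 6.0%. The same formula gives 5.1% at p = 2% and 5.3% at p = 5%.

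**5. Direction.** If detached patients swell 0.5 SD less, the same bias runs against tape. If detachment is unrelated to swelling and there is no true effect, the bias is zero.

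**The case against.** The strongest defence is the wording itself. What is to be substituted is data that are missing, and nothing says a measured value is to be deleted. The sentences just before promise intention-to-treat and list the only permitted exclusions. The detachment words can be read as their counterpart: such patients stay in, with imputation for anything they lack. This stands. It is a fair reading, and on it there is no bias. Only the detachment limb would then be redundant; the rule for non-evaluable endpoints would still do its work.

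A reader might infer instead that the plan clearly intends to discard measured values, pointing to *and/or*, to the dedicated 48-hour field, and to a cut-off that matches the lower end of the period in "Even though tape results could be seen after 2-3 days, we choose to collect T1 variables (as previously described) at day 7". The documents do not support so firm a conclusion. Table 2 also holds a general removal field that no analysis rule uses, so a field may be there only for description. The sentence on 2–3 days explains the timing of T1 and does not mention detachment. These points keep the first reading open without making it the better one.

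A reader might also infer that the primary result will favour tape, or that the type I error will be seriously inflated. Neither follows. An error near 10% needs both 20% early detachment and a 0.5 SD gap in swelling, and the documents give neither figure.

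**Conclusion.** The concern holds as an ambiguity in the primary-analysis rule, with a real consequence on one of two tenable readings. Applied as a separate trigger, early detachment replaces measured outcomes in one arm because of a post-randomisation event, which conflicts with the intention-to-treat promise in the same paragraph. Limited to values not obtained, it is redundant and harmless. The plan does not choose.

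The size cannot be fixed from the documents. It rests on the detachment rate, on any link between detachment and swelling, and on the imputation model, none of which is given. A discrepancy of around 0.04 to 0.05 SD at 10% early detachment is a conditional illustration and should not be read as a forecast. If early detachment is rare, the practical effect is negligible.

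**What to change.** Remove tape detachment as an imputation trigger and state: *T1 values are analysed as measured whether or not the tape detached; only values not obtained are imputed, in either arm.* If the effect with tape retained for at least 48 hours is of interest, make it a labelled supplementary analysis, using the 48-hour field already in Table 2.

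This changes plan text only and needs no new data. The cost is possible dilution. If benefit is lost on detachment, the analysis targets 0.40 × (1 − 0.10) = 0.36 SD at an assumed 10% early detachment. Power at 100 per arm is then about 72%, against the planned 80% and about 78% under within-arm imputation; restoring 80% would need 123 per arm. At 5% detachment, power is about 76%. That lower figure is the power for the effect of assignment, which is what the plan says it will estimate.

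### Two primary circumference endpoints serve one hand-oedema aim, each tested at 0.05 with no success rule or multiplicity control, so alpha 0.05 and power 0.80 hold together only per endpoint

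*Combined protocol and SAP*

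**What the plan says.** The Aim section states one primary question: whether tape "is able to reduce the formation of hand oedema, compared to the untreated controls". The Primary endpoints section then names two variables. The first is the change in thumb circumference over the seven days of follow-up. The second is given as "ii) difference in the circumference of the remaining 4 fingers merged together, between T0 and T1".

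The Sample size calculation section gives one calculation, with "effect size: 0.4, error α = 0.05, power = 0.80 and allocation ratio = 1", leading to 100 evaluable and 110 enrolled patients per arm. It does not tie the 0.4 to either circumference or to a joint criterion.

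The Statistical analysis section compares group means for "the T0-T1 differences of circumference of both thumb" and the other four fingers by independent-groups t-test. It closes with one threshold for everything: "We will perform all analyzes using 2-tailed tests and consider significant a p value <0.05".

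No section says whether one or both primary endpoints must be significant. None ranks them, splits alpha or names an adjustment.

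**The concern.** Two tests feed one claim, and each is allowed the full 5%. If a single significant circumference is taken as showing that tape reduces hand oedema, the chance of claiming an effect when there is none exceeds 5%. If both are needed, the trial is less likely to succeed than the stated 80%.

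Because the rule is unstated, it could also be settled after seeing which endpoint worked. A mixed result, with one circumference significant and the other not, has no predefined interpretation. That gap sits on the primary question and cannot be credibly closed once results are known.

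**Working it through.** **Inputs.** From Sample size calculation: standardised effect d = 0.4, alpha 0.05, power 0.80, 1:1 allocation, n = 100 evaluable per arm. From Statistical analysis: two-sided t-tests at 0.05. Not in the documents: the correlation r between the two endpoints (0, 0.5 and 0.9 are assumed) and whether d = 0.4 applies to both endpoints (assumed unless stated).

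**1. Reproduce the plan's figure.** Normal formula: n = 2(1.960 + 0.842)² / 0.4² = 98.1, so 99 per arm. The noncentral t solution is 99.08, so 100 per arm. The plan's figure is therefore a single-endpoint, two-sided calculation at the full 0.05. At n = 100 the noncentrality is 0.4 × √(100/2) = 2.83, and t-test power is 0.8036 at alpha 0.05 and 0.7153 at alpha 0.025.

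**2. Success on either endpoint, unadjusted.** With no effect on either endpoint, family-wise error = 1 − P(both |Z| < 1.96). At r = 0 this is 1 − 0.95² = 0.0975. Counting only false claims of benefit, it is 1 − 0.975² = 0.0494, against 0.025 for one test. Other values of r use the bivariate normal. Power for at least one is 2 × 0.8036 − P(both); for example, at r = 0.5 it is 1.607 − 0.691 = 0.916.

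**3. Success only if both are significant.** At r = 0 power is 0.8036² = 0.646. Other values come from the bivariate normal with mean 2.83 on both endpoints, checked by 400,000 simulated pairs of t-tests.

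**4. Holm at family-wise 0.05.** An endpoint succeeds if its p < 0.025, or if its p < 0.05 and the other endpoint's p < 0.025. At r = 0, power per endpoint is 0.7153 + (0.8036 − 0.7153) × 0.7153 = 0.778. Power for at least one is 1 − (1 − 0.7153)² = 0.919.

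| Quantity | r = 0 | r = 0.5 | r = 0.9 |
|---|---|---|---|
| Either rule: family-wise error | 9.75% | 9.1% | 7.0% |
| Either rule: false benefit claims only | 4.9% | 4.5% | 3.5% |
| Either rule: power for at least one | 96% | 92% | 85% |
| Both rule: power, normal | 65.2% | 69.7% | 75.9% |
| Both rule: power, simulated t-tests | 64.7% | 69.1% | 75.4% |
| Holm: power per endpoint, d = 0.4 on both | 77.9% | 76.8% | 75.4% |
| Holm: power for at least one, d = 0.4 on both | 91.9% | 85.5% | 77.7% |
| Holm: power for one endpoint, other null | 71.9% | 71.6% | 71.6% |

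Error rates are from the bivariate normal and Holm rows from simulated t-tests; the two methods agree within about one percentage point.

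**5. Sensitivity to the effect on the second endpoint.** If the second effect were only 0.2 (an illustrative value with no source in the documents), power under the both rule would be 23%, 27% and 29%. This shows why the plan should say which endpoint the 0.4 refers to.

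**The case against.** The strongest reply is that no stated figure is wrong. The sample size is correct for each endpoint, and the Statistical analysis section labels the two comparisons separately, so they may be meant as two distinct claims, each with its own 5%. That reading is possible, but the protocol does not state it, and its one primary aim concerns the hand.

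A second reply is that the conjunction joining endpoints (i) and (ii) already means both are required. The secondary endpoints are listed in the same way, where no joint rule is plausible. If both were intended, 80% would overstate the power for that criterion.

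Third, correlation softens the inflation. This is right: "OER nurses will evaluate the extent of oedema in the fracture-homolateral hand by measuring the circumference" describes two readings on one hand at the same visits, so positive correlation is likely and 9.75% is an upper limit rather than an expected value. At r = 0.9 the error is still 7.0%.

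Fourth, both endpoints are prespecified, the analyst does not know which group is which, and reporting is to follow a trial guideline. These safeguards make it harder to drop an endpoint. They do not say what counts as success, and masked group labels do not hide which p-value is small.

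It is also fair that the either rule damages only alpha, since power for at least one endpoint is then above 0.80, and that the both rule damages only power.

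**Conclusion.** The concern holds. Alpha 0.05 and power 0.80 are assured together only for each circumference taken alone, and the power only if d = 0.4 applies to that circumference. For the single hand-oedema claim, the either rule gives a family-wise error of about 7.0% to 9.75%, and the both rule gives power of about 65% to 75%. These ranges assume correlations from 0 to 0.9, and the power range also assumes d = 0.4 on both endpoints. The inflation is moderate. The absence of a success rule depends on none of these assumptions, and it should be corrected before the analysis.

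**What to change.** Keep 220 patients. Before any results are seen, state one success rule in the Statistical analysis section and restate power to match:

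- **A. Either endpoint supports the hand-oedema claim.** Test the two primaries by Holm at family-wise two-sided 0.05. State power as about 72% per endpoint if the other has no effect; with d = 0.4 on both, about 75–78% per endpoint and 78–92% for at least one.
- **B. Both endpoints are required.** Keep 0.05 for each and state power as about 65–75%, assuming d = 0.4 on both.
- **C. Two separate claims.** Say so, limit each conclusion to its own circumference, and draw no overall hand-oedema conclusion from one result. If the hand claim would then need both results, this becomes option B and carries its power.

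In every case, state which endpoint the 0.4 refers to and that secondary endpoints are supportive.

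The cost is two or three sentences and, under A or B, a less favourable stated power. Restoring 80% per endpoint at the first Holm step (alpha 0.025) would need 121 evaluable patients per arm instead of 100, but the fix does not require it.
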